9.7. Electrocardiograms

Standard supine 12-lead ECGs will be performed by qualified technicians in triplicate on the ECG machine dedicated to this study. Electrocardiograms will be reviewed at the site for treatment of any urgent issues. The clinical significance of any ECG change must be assessed by the Investigator in the context of the subject's medical history, physical examination, and concomitant medications. The Investigator or delegated physician will review, sign, and date all ECGs.

9.8. Physical Findings

A complete physical examination, with the exception of the genitourinary system and prostate, will be performed on each subject at baseline prior to dosing, at discharge, and at the follow up visit on Day 30.

Body weight will be measured (or best estimated if not feasible to measure) for all subjects prior to enrollment for qualification.

9.9. Other Safety Assessments

9.9.1. Bleeding

Bleeding will be assessed and categorized as sICH, any ICH, or non-ICH major bleeding (as defined by TIMI criteria). All bleeding events will be assessed by the Principal Investigator. In addition, any ICH event will be centrally assessed by 2 external blinded reviewers (1 neuroradiologist and 1 neurologist). This review is independent of the Principal Investigator's assessment.

All sICH events will be classified according to clinical and CT criteria. Hemorrhagic infarction 1 (HI1) is defined as small petechiae along the margins of the infarct; hemorrhagic infarction 2 (HI2) is defined as confluent petechiae within the infarcted area but no space-occupying effect; parenchymal hemorrhage (PH1) is defined as blood clots in 30% or less of the infarcted area with some slight space-occupying effect; and parenchymal hemorrhage (PH2) is defined as blood clots in more than 30% of the infarcted area with substantial space-occupying effect. Symptomatic intracranial hemorrhage is defined as (European Cooperative Acute Stroke Study [ECASS] criteria²) blood at any site in the brain on the CT scan (as centrally assessed by the external blinded reviewers, independent of the assessment by the Investigator), documentation by the Investigator of clinical deterioration, or adverse events indicating clinical worsening (eg, drowsiness, increase of hemiparesis) or causing a decrease in the NIHSS score of 4 or more points, and intracranial hemorrhage is determined as the predominant cause of clinical deterioration.

Non-ICH major bleeding is defined as (TIMI hemorrhage criteria) clinically significant overt signs of hemorrhage associated with a drop in hemoglobin of > 5 g/dL (or, when hemoglobin is not available, an absolute drop in hematocrit of $> 15\%$).

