4.1.1. Inclusion Criteria

Subjects must satisfy all of the following criteria to be included in the study:

1. Subjects have a clinical diagnosis of ischemic stroke MCA occlusion (M1 or M2), as demonstrated by CT or MR angiography.
2. Men and women 18 to 80 years of age, inclusive.
3. Subjects have stroke symptom onset within 3 to 8 hours before initiation of study drug administration. For subjects with a wake-up stroke, symptom onset time refers to the last time the subject was known to be well.
4. Subjects have a NIHSS score > 4 and < 22 .
5. Subjects have a body weight of 50 kg to 120 kg, inclusive.
6. Subjects, or their legally authorized representative, must give written informed consent to participate in the study prior to participating in any study-related procedures. A separate written informed consent is required for collecting a blood sample for genotyping.

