11.6.6.2. Neurologic function

Neurologic function will be assessed using the NIHSS. Raw values of the NIHSS score will be presented graphically by subject, and will also be summarized by treatment. Change from baseline values will be summarized. The number and percentage of subjects of 0 or 1 point of postdose NIHSS and 4 points or more improvement of NIHSS will be tabulated by scheduled time of evaluation and treatment. Pooled placebo data of all cohorts will be summarized.

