11.9. Data and Safety Monitoring Board

Two external reviewers (1 neurologist and 1 neuroradiologist), who are not involved in the study conduct and are blinded to the treatment assignments, will assess all cases of ICH. The neuroradiologist will review all CT or MR scans (independent to the Investigator at site), and classify any ICH findings according to the ECASS morphologic definitions.

The neurologist will assess whether neurologic deterioration is due to ICH, or other causes.

Dose Escalation Safety Data Review:

Blinded clinical (bleeding and other AEs) and safety laboratory data of each completed dose level will be reviewed prior to escalation to the next dose level. The dose escalation decision will be made based on this data review. Participants in the dose escalation safety data review meetings are the following: Clinical Study Leader, Medical Monitors from the Sponsor and PAREXEL, external reviewers for ICH, Clinical Study Manager, and Statistician from the Sponsor.

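### The only numeric criterion in the sICH definition (Section 9.9.1) treats a fall in NIHSS as worsening, while Section 11.6.6.2 implies that a fall is improvement

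*Combined protocol and SAP*

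**What the plan says.** Section 9.9.1 contains the only definition of sICH. It requires blood in the brain on CT, as assessed centrally, together with one of three signs of worsening:

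- deterioration documented by the Investigator;
- adverse events that indicate clinical worsening, with drowsiness and increasing hemiparesis as examples;
- events "causing a decrease in the NIHSS score of 4 or more points".

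It then adds the condition that "intracranial hemorrhage is determined as the predominant cause of clinical deterioration".

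Section 11.6.6.2 sets out the NIHSS analysis. It tabulates, by time and treatment, "The number and percentage of subjects of 0 or 1 point of postdose NIHSS and 4 points or more improvement of NIHSS".

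Inclusion criterion 4 in Section 4.1.1 fixes the starting range: "Subjects have a NIHSS score > 4 and < 22".

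Sections 3.1.2, 3.1.6 and 11.10 use the term sICH for cohort expansion and for stopping escalation, without defining it again.

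**The concern.** A fall of 4 or more points cannot be a sign of deterioration in one section and an improvement in another. Read literally, a subject whose NIHSS rises after a hemorrhage can never meet the one limb that has a number attached, while a subject whose score falls by 4 or more points does meet it.

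This would be a small editorial matter in most places, but sICH is the event on which escalation turns, and single cases count:

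- One case among the first 6 active-treated subjects of Cohort 1 or 2 triggers an expansion cohort (Section 3.1.2).
- Two cases in active-treated subjects at a dose level, or 4 cumulatively, stop escalation (Sections 3.1.6 and 11.10).

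About 40 sites are planned, and two external reviewers assess intracranial hemorrhage. Each must notice the reversed limb and then correct it or ignore it. Nothing in the documents provided tells them to do so in the same way.

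**Working it through.** The plan states no figure for this limb, so there is none to reproduce. The nearest figure is the stopping threshold: 2/12 = 16.7%, which agrees with the incidence of about 16% cited in Section 11.10. That agreement does not depend on the NIHSS wording. The question here is one of direction.

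**Step 1. Entry scores.** Section 4.1.1 requires a score above 4 and below 22. Assuming whole-point scores, entry runs from 5 to 21, which is 21 − 5 + 1 = 17 values.

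**Step 2. The fall needed to reach the 0-or-1 category of Section 11.6.6.2.** Fall = entry score − postdose score.

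| Case | Calculation | Fall |
|---|---|---|
| Smallest | 5 − 1 | 4 |
| Largest | 21 − 0 | 21 |

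There are 17 × 2 = 34 combinations of entry score and postdose score, and all 34 are falls of 4 or more points.

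**Step 3. From fall to improvement.** This step is a reading of the text, not arithmetic. Section 11.6.6.2 sets the 0-or-1 category beside an improvement of 4 or more points. Every subject in that category has fallen by at least the amount that Section 9.9.1 counts as worsening. The mRS is handled in a parallel way: Section 11.7 tabulates postdose scores of 0 or 1, and exclusion criterion 18 treats a score above 1 as preexisting disability, so 0 or 1 is the favorable end there. No section says that a lower NIHSS is worse.

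**Step 4. What the literal text does.**

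| Course after a centrally confirmed hemorrhage | Numeric limb as written | Rest of the definition |
|---|---|---|
| NIHSS rises by 4 or more | Not met | Can still qualify through Investigator-documented deterioration or a worsening adverse event |
| NIHSS falls by 4 or more, improvement only | Met | Should fail, because there is no deterioration for the hemorrhage to have caused |

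The text therefore loses a usable numeric threshold for worsening. It does not lose every route by which a true case can be counted.

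**Step 5. When the limb can operate.** The sICH window is 36 hours from the start of infusion (Section 3.1.6). Fixed NIHSS assessments fall at predose, 6 hours and 24 hours (Sections 6.1.1, 6.1.5 and 6.2). The next is on Day 5, at 96 hours, or at earlier discharge (Section 6.5). The last 36 − 24 = 12 hours have no fixed score, so in that period the limb depends on a discharge or unscheduled score. This is so under either wording, and correcting the sentence does not change it.

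**The case against.** The strongest reply is that the error does no harm in practice.

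- **False positives are blocked.** The sentence itself requires hemorrhage to be the predominant cause of deterioration, so a subject who only improves should not be counted.
- **False negatives are unlikely.** The other two limbs have no threshold, and a hemorrhage that raises the NIHSS by 4 points would ordinarily fall under one of them.
- **Central review does not use the cut-off.** Section 11.9 gives one neurologist and one neuroradiologist all cases of intracranial hemorrhage, and "The neurologist will assess whether neurologic deterioration is due to ICH, or other causes".
- **Escalation has further protection.** Section 11.9 states that "Blinded clinical (bleeding and other AEs) and safety laboratory data of each completed dose level will be reviewed prior to escalation". The participants include the "external reviewers for ICH, Clinical Study Manager, and Statistician from the Sponsor". Section 3.1.6 also allows escalation to be halted outside the prespecified rules.
- **Other documents may already be right.** Section 11 leaves detailed methods to a separate analysis plan. Neither that plan nor any reviewers' instructions is reproduced in the text examined here, so they cannot be said to repeat the error.

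All of this stands as a limit on the likely effect. No event has been shown that would be counted differently, and the count of 34 combinations establishes direction only, not an effect size. None of it makes the sentence right. If decrease was meant loosely as decline, the text still says that the score decreases, and the score is a number. The safeguards work by readers setting the limb aside, which is a reason to correct it.

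**Conclusion.** The inconsistency is real and should be fixed. The only numeric limb of the sole sICH definition runs opposite to the direction implied by Section 11.6.6.2 and the entry range, and no other section corrects it. It reads as a drafting error and not as a design choice.

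The conclusion rests on whole-point NIHSS scores and on reading the pairing in Section 11.6.6.2 as showing that lower is better. Confidence is high for the wording error only. It does not extend to any effect on sICH counts or stopping decisions, and the documents do not support an estimate of the share of cases missed.

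A separate, minor mismatch sits in the same sentence of Section 9.9.1. It requires blood on CT, while Section 11.9 has the neuroradiologist read CT or MR scans. This does not add to the weight of the main point.

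**What to change.** Reconcile Section 9.9.1 with Section 11.6.6.2 so that the NIHSS limb of the sICH definition denotes worsening in the direction that the analysis section implies. Use identical text in the statistical analysis plan and in the instructions to the two external reviewers, so that sites and central readers apply one definition. As a separate small edit, align the CT-only imaging condition in Section 9.9.1 with the CT-or-MR reading in Section 11.9.

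The cost is a correction to one sentence, repeated in those two documents. The 4-point threshold, the stopping rules, the sample size, the visit schedule and the data collected all stay as they are.

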4.1.2. Exclusion Criteria

Subjects who meet any of the following criteria will be disqualified from entering the study:

1. Subjects have evidence of intracranial hemorrhage on noncontrast CT (or MR).
2. Subjects have symptoms of subarachnoid hemorrhage, even with normal CT.
3. Subjects have evidence of large MCA territory infarction (sulcal effacement or blurring of gray-white junction in greater than 1/3 of MCA territory).
4. Subjects have prior non-traumatic intracranial hemorrhage.
5. Subjects have known arteriovenous malformation or aneurysm.
6. Subjects have evidence of active bleeding.
7. Subjects have platelet count < 100,000.
8. Subjects have INR > 1.7.
9. Subjects have used heparin within 48 hours or have an elevated partial thromboplastin time.
10. Subjects have used a nonvitamin K antagonist oral anticoagulant such as dabigatran, rivaroxaban, apixaban, or other factor Xa inhibitors within 48 hours.
11. Subjects have used fondaparinux or low molecular weight heparin at an anticoagulation dose within 48 hours.
12. Subjects with anticipated use of heparin, or fondaparinux or low molecular weight heparin, or nonvitamin K antagonist oral anticoagulant such as dabigatran, rivaroxaban, apixaban, or other factor Xa inhibitors within 48 hours of randomization.
13. Subjects have blood pressure > 185/110 mmHg, or require aggressive medication to maintain blood pressure below this limit (routine medical treatment is allowed to lower the blood pressure below this limit).
14. Subjects have had intracranial surgery, clinically significant head trauma (in the opinion of Principal Investigator), Alteplase treatment, or a previous stroke within 3 months.
15. Subjects have had major surgery within 14 days.
16. Subjects have had gastrointestinal or genitourinary bleeding in the last 21 days.
17. Subjects have had a lumbar puncture (or epidural steroid injection) within 14 days.
18. Subjects have a preexisting disability classified by mRS > 1.
19. Subjects have an estimated glomerular filtration rate (using Modification of Diet in Renal Disease [MDRD] equation) < 60 mL/min/1.73 m².
20. Subjects have baseline hemoglobin < 10.5 g/dL.

21. Subjects have a positive pregnancy test. Serum pregnancy tests will be performed in women of childbearing potential (childbearing potential is assumed in women up to 55 years of age).

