11.6.1. Adverse Event Analyses

Results from placebo subjects will be pooled across cohorts.

A TEAE is defined as an adverse event that: emerges during the treatment period (from first dose date until 30 days after the last dosing date), having been absent at predose; or reemerges during treatment, having been present at baseline but stopped prior to treatment; or worsens in severity after starting treatment relative to the predose state, when the adverse event is continuous.

Adverse events will be coded using Medical Dictionary for Regulatory Activities (MedDRA) and will be summarized and listed by treatment, System Organ Class (SOC), and preferred term.

The number and percentage of subjects reporting TEAEs will be tabulated by SOC and preferred term.

Similarly, the number and percentage of subjects reporting treatment emergent SAEs will be tabulated, as well as TEAEs/SAEs considered related to DS-1040b.

A by subject adverse event (including TEAEs) data listing including, but not limited to, verbatim term, preferred term, SOC, and relationship to study drug will be provided.

Deaths, other SAEs, and other significant adverse events, including those leading to permanent discontinuation from DS-1040b, will be listed.

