11.6.6. Other Safety Analyses

11.6.6.1. Bleeding

Bleeding events will be summarized as the following categories: sICH, any ICH, or non-ICH major bleeding. The number and percentage of subjects experiencing these bleeding events will be tabulated by treatment. Results from placebo-treated subjects will be pooled across cohorts.

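### The written definition of non-ICH major bleeding does not say how transfusion is handled, and no table row counts subjects with any non-ICH bleeding by dose

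*Combined protocol and SAP*

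**What the plan says.** Section 9.9.1 sorts bleeding into three categories: sICH, any ICH, and non-ICH major bleeding. The third requires "clinically significant overt signs of hemorrhage associated with a drop in hemoglobin of > 5 g/dL". Where no hemoglobin value exists, a hematocrit fall above 15 percentage points serves instead. The TIMI criteria are named as the source. The section does not mention transfusion, and nor does any other part of the documents. "All bleeding events will be assessed by the Principal Investigator"; the external reviewers look at ICH only.

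Section 11.6.6.1 carries the same three categories into the analysis: "Bleeding events will be summarized as the following categories: sICH, any ICH, or non-ICH major bleeding". It adds: "The number and percentage of subjects experiencing these bleeding events will be tabulated by treatment".

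Section 3.1.6 uses non-ICH major bleeding, again by reference to TIMI, as a criterion for stopping escalation: two cases in active-treated subjects at a dose level, during hospitalization and up to 5 days from the start of infusion.

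Bleeding that does not reach the major category goes through Section 11.6.1, where adverse events are "summarized and listed by treatment, System Organ Class (SOC), and preferred term".

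**The concern.** The primary objective is safety, and Section 1.3 says that nonclinical results suggest the drug may enhance fibrinolysis. Bleeding by dose is therefore a result that readers will look for first. Two features of the plan weaken it.

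First, the major category depends on a measured fall. Red cells given for a bleed raise both hemoglobin and hematocrit, so treating the bleed reduces the quantity that decides whether it counts. The hematocrit fallback has the same gap. The category feeds a table row and also a rule that governs escalation, so an uncounted case matters in both places.

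Second, between major bleeding and single preferred terms there is no intermediate summary. A nosebleed, a urinary bleed and an infusion-site bleed in three subjects at one dose would appear as three single events in three organ classes. In groups of 6 or 12 active subjects, a rise with dose is easier to see in one row that counts each subject once.

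**Working it through.** **Plan's own figure.** There is none for non-ICH bleeding: the documents give no rate, power or sample-size argument for it. The nearest is the sICH benchmark of about 16% in Section 11.10, which matches its rule (2/12 = 16.7%). I use 16.7% below only as one point on a scale, not as an expected rate of non-ICH bleeding.

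**Step 1: the threshold.** Section 4.1.2 excludes a subject if "Subjects have baseline hemoglobin < 10.5 g/dL". A subject entering at that floor counts on the hemoglobin limb only if the measured value falls below 10.5 − 5 = 5.5 g/dL. From 12 g/dL the level is 7; from 14 g/dL it is 9.

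**Step 2: effect of transfusion on the measured fall.** Measured fall = true loss − units × rise per unit. The rise per unit is not in the documents; I assume 0.5 to 1.5 g/dL. I also assume that the lowest recorded value comes after the units are given. A case counts if the measured fall exceeds 5 g/dL.

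| True loss (g/dL) | Units | Measured fall at 0.5 / 1.0 / 1.5 g/dL per unit | Counted? |
|---|---|---|---|
| 6 | 2 | 5.0 / 4.0 / 3.0 | no / no / no |
| 7 | 2 | 6.0 / 5.0 / 4.0 | yes / no / no |
| 8 | 2 | 7.0 / 6.0 / 5.0 | yes / yes / no |
| 8 | 3 | 6.5 / 5.0 / 3.5 | yes / no / no |

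Without transfusion, every one of these losses would count.

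**Step 3: effect on the two-case count.** Let p be the true rate of major non-ICH bleeding and m the share that transfusion takes below the threshold. Both are assumptions. With n = 12 active subjects and q = p(1 − m):

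P(at least 2) = 1 − (1 − q)^12 − 12q(1 − q)^11.

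At p = 1/6 and m = 0: 1 − 0.112 − 0.269 = 0.619. At p = 1/6 and m = 0.5, q = 1/12: 1 − 0.352 − 0.384 = 0.264.

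| Assumed p | m = 0 | m = 25% | m = 50% | m = 75% |
|---|---|---|---|---|
| 5% | 0.118 | 0.072 | 0.035 | 0.009 |
| 10% | 0.341 | 0.226 | 0.118 | 0.035 |
| 16.7% | 0.619 | 0.453 | 0.264 | 0.087 |
| 20% | 0.725 | 0.557 | 0.341 | 0.118 |
| 30% | 0.915 | 0.789 | 0.557 | 0.226 |

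For comparison, 6 active subjects (the initial size of Cohorts 1 and 2) at p = 16.7% with no masking give 0.263. Masking half of the cases in a 12-subject group costs about as much as halving the group.

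**Step 4: the tables side by side.** Section 11.6.6.1 gives three rows, two of them intracranial. Section 11.6.1 gives subjects by organ class and preferred term. Neither yields the number of subjects at a dose with at least one non-ICH bleed, and the preferred-term rows cannot simply be added, because one subject may appear in several.

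**The case against.** The strongest reply is that nothing is lost from the trial, and much of that stands.

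- A reader might infer that lesser bleeding is never totalled by dose. The documents do not support this: Section 11.6.1 counts subjects by treatment for each term and organ class, and does likewise for serious and related events. Only the combined count is absent.
- A reader might infer that a serious transfused bleed would be missed altogether. It would not. It can qualify as an SAE under Section 9.2.2, is then reported with a narrative covering treatment and laboratory data (Section 9.3.1), and is tabulated. Section 11.9 puts bleeding and laboratory data for each completed dose level before the escalation review, and Section 3.1.6 allows escalation to be halted outside the listed criteria.
- Section 11.6.2 summarizes hematology and its change from baseline by treatment, whatever the 5 g/dL threshold. This stands in part: those values are also as measured after any transfusion, and Section 6 schedules postdose hematology only at 24 and 48 hours.
- A reader might infer that the major category will almost always be empty. That rests on an assumed rate. At 1% to 2%, the chance of no case, (1 − p)^n, is 0.89 to 0.79 in 12 active subjects, 0.62 to 0.38 in 48 (the planned minimum) and 0.55 to 0.30 in 60. These figures reflect small cohorts, not the definition.
- The TIMI source may itself deal with transfusion. That cannot be checked from the documents; what can be said is that the operative text is silent.
- Section 11 defers detail to a later analysis plan, and the eCRF is not shown. Extra rows or a transfusion field may exist there. The stopping count operates during the study, however, so it cannot wait for a plan that need only be final before database lock.

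**Conclusion.** The point holds in a limited form. Followed literally, Section 9.9.1 lets a transfused major bleed fall out of one table row and one stopping count, while it stays visible elsewhere in the safety data. The plan also lacks a subject-level count of any non-ICH bleeding by dose.

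The size depends on assumptions. With 0.5 to 1.5 g/dL per unit, a true 6 g/dL loss treated with 2 units is not counted anywhere in that range; larger losses may or may not be. If half of major bleeds were masked, the chance of meeting the two-case rule in 12 active subjects would fall from 0.34 to 0.12 at a true rate of 10%, and from 0.62 to 0.26 at 16.7%. The documents give neither the true rate nor the masked share, so these figures show the direction and possible scale, not an expected loss.

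The documents do not show that a bleeding signal would go unseen. The case for change is that the primary safety objective gains a clearer count from data that are mostly collected already.

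**What to change.** 1. Record red-cell units and times for each subject, if the eCRF does not already do so. Report the hemoglobin or hematocrit change for each bleed both as measured and corrected for units given, with the correction per unit fixed in advance. Give both versions to the escalation review.
2. Reconcile Sections 3.1.6, 9.9.1 and 11.6.6.1 so that all three state which version is counted. The escalation criterion itself remains the sponsor's decision.
3. In Section 11.6.6.1, add two subject-level rows for each dose and for pooled placebo: any non-ICH bleeding adverse event, from a prespecified term list, and non-ICH bleeding that was serious, fatal or transfused.

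The cost is at most one eCRF field, a short term list and two table rows; adverse events and hemoglobin are already collected. The drawback is that more low-grade events will be on display, so the any-bleeding row should be read beside the pooled placebo column. Items 1 and 2 should be settled before the next escalation decision, item 3 before database lock.
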